#### 4.1.5.2 Procedures for emergency unblinding

For blinded trials, the investigator will be supplied with a set of sealed envelopes containing the medication codes for each subject according to the randomisation scheme. The envelopes will be kept unopened at the trial site until the end of data collection. An envelope may only be opened in emergency situations when the identity of the trial drug must be known to the investigator in order to provide appropriate medical treatment or to assure safety of trial participants. If the envelope for a subject is opened, the sponsor must be informed immediately. The reason for opening the code break must be documented on the envelope or appropriate CRF page along with the date and the initials of the person who broke the code. At the close-out visit all envelopes are collected.

#### 4.1.6 Packaging, labelling, and re-supply

Drug supplies will be provided by the Department of Pharmaceutical Development of Boehringer Ingelheim Pharma GmbH & Co. KG, Biberach, Germany.

The clinical trial supply consists of containers holding the trial medication which are labelled with trial identification. The required information according to Annex 13/EU GMP Guideline will be provided on the containers. Smaller boxes within the clinical trial supply containers will be labelled with:

- BI trial number
- Name of product and strengths or identification code
- Pharmaceutical dosage form, quantity of dosage units
- Route and mode of administration
- Term 'For Clinical Trial Use' (domestic language)
- Sponsor name and address
- Storage conditions

- Use-by date
- Batch
- Investigator

The vials are labelled with reduced requirements.

The telephone number of the sponsor and name, address and telephone number of the trial site are given in the subject information form. Examples of the labels will be available in the ISF.

Re-supply is planned.

#### 4.1.7 Storage conditions

Drug supplies will be kept in their original packaging and in a secure limited access storage area according to the recommended (labelled) storage conditions. Where necessary, a temperature log must be maintained to make certain that the drug supplies are stored at the correct temperature. If the storage conditions are found to be outside the specified range, the local clinical monitor (as provided in the list of contacts) is to be immediately contacted.

#### 4.1.8 Drug accountability

The investigator / pharmacist / investigational drug storage manager will receive the investigational drugs delivered by the sponsor when the following requirements are fulfilled:

- Approval of the study protocol by the IRB / ethics committee
- Availability of a signed and dated clinical trial contract between the sponsor and the Head of Trial Centre
- Approval/notification of the regulatory authority, e.g. competent authority
- Availability of the curriculum vitae of the principal investigator
- Availability of a signed and dated clinical trial protocol or immediately imminent signing of the clinical trial protocol

Only authorised personnel as documented in the form 'Site Delegation Log' may dispense medication to trial subjects. The trial medication must be administered in the manner specified in the CTP. All unused medication will be disposed locally by the trial site upon written authorization by the clinical monitor. Receipt, usage and disposal must be documented on the respective forms. Account must be given for any discrepancies.

The investigator / pharmacist / investigational drug storage manager must maintain records of the product's delivery to the trial site, the inventory at the site, the use by each subject, and the return to the sponsor or alternative disposal of unused products.

These records will include dates, quantities, batch / serial numbers, expiry ('use-by') dates, and the unique code numbers assigned to the investigational products and trial subjects. The investigator / pharmacist / investigational drug storage manager will maintain records that document adequately that the subjects were provided the doses specified by the CTP, and that reconcile all investigational products received from the sponsor. At the time of disposal, the

investigator / pharmacist / investigational drug storage manager must verify that no remaining supplies are in the investigator's possession.

## 4.2 CONCOMITANT THERAPY, RESTRICTIONS, AND RESCUE TREATMENT

### 4.2.1 Rescue medication, emergency procedures, and additional treatments

There are no specific rescue drugs foreseen for the treatment of AEs. No special emergency procedures are to be followed. No additional treatment is planned. However, in case of adverse events in need of treatment, the investigator can authorise symptomatic therapy. In those cases, subjects will be treated as necessary and, if required, kept under supervision at the trial site or transferred to a hospital until all medical evaluation results have returned to an acceptable level.

### 4.2.2 Restrictions

#### 4.2.2.1 Restrictions regarding concomitant treatment

In principle, no concomitant therapy is allowed. All concomitant or rescue therapies will be recorded (including time of intake on study days) on the appropriate pages of the CRF.

#### 4.2.2.2 Restrictions on diet and life style

While admitted to the trial site the subjects are restricted from consuming any other foods or drinks than those provided by the staff. Standardised meals will be served at the time points described in the [Flow Chart](#). On Day 1 for all subjects and on Day 8, Day 15 and Day 22 for subjects receiving multiple doses of BI 655130, no food is allowed for at least 10 h before and 1.5 h after administration of the study drug (= end of infusion).

On all days of drug administration, starting from 1 hour before drug administration until 1.5 h after end of infusion liquid intake is not allowed. From breakfast until 24 hours post-dose water intake will be within 1000 to 3000 mL. Total fluid intake on all 24 hours inhouse days is recommended to be at least 1.5 liters and should not exceed 3.5 liters.

Smoking is not allowed during in-house confinement at the trial site. On the ambulatory days it is restricted to not more than 10 cigarettes or 3 cigars or 3 pipes per day

Methylxanthine-containing drinks or foods (such as coffee, tea, cola, energy drinks, and chocolate) are not allowed during inhouse confinement. Alcoholic beverages are not permitted starting 7 days before the first administration of trial medication until Day 28. From Day 28 onwards, alcohol consumption is restricted to 20 g alcohol per day corresponding to 0.5 L beer or 0.2 L of white wine per day.

Excessive physical activity (such as competitive sport) should be avoided starting 7 days before the first administration of trial medication until the end of trial examination.

Direct exposure to the sun or exposure to solarium radiation should be avoided during the entire study.

#### **4.3 TREATMENT COMPLIANCE**

Compliance will be assured by administration of all trial medication in the study centre under supervision of the investigating physician or a designee. The measured plasma concentrations will provide additional confirmation of compliance.

Subjects who are non-compliant (for instance, who do not appear for scheduled visits or violate trial restrictions) may be removed from the trial and the CRF will be completed accordingly (for further procedures, please see [Section 3.3.4.1](#)).

## **5. VARIABLES AND THEIR ASSESSMENT**

### **5.1 EFFICACY - CLINICAL PHARMACOLOGY**

#### **5.1.1 Endpoints of efficacy**

No efficacy endpoints will be evaluated in this trial.

#### **5.1.2 Assessment of efficacy**

Not applicable.

## **5.2 SAFETY**

#### **5.2.1 Endpoints of safety**

Primary endpoint to assess safety and tolerability of BI 655130 is the number [N (%)] of subjects with drug-related AEs.

Further criteria of interest:

- AEs (including clinically relevant findings from the physical examination)
- Safety laboratory tests
- 12-lead ECG
- Continuous ECG monitoring
- Vital signs (blood pressure, pulse rate)

#### **5.2.2 Assessment of adverse events**

##### **5.2.2.1 Definitions of adverse events**

###### **Adverse event**

An adverse event (AE) is defined as any untoward medical occurrence in a patient or clinical investigation subject administered a medicinal product and which does not necessarily have to have a causal relationship with this treatment.

An AE can therefore be any unfavourable and unintended sign (including an abnormal laboratory finding), symptom, or disease temporally associated with the use of a medicinal product, whether or not considered related to the medicinal product.

###### **Adverse reaction**

An adverse reaction is defined as a response to a medicinal product which is noxious and unintended. Response in this context means that a causal relationship between a medicinal product and an adverse event is at least a reasonable possibility. Adverse reactions may arise from use of the product within or outside the terms of the marketing authorisation or from occupational exposure. Conditions of use outside the marketing authorization include off-label use, overdose, misuse, abuse and medication errors.

### Serious adverse event

A serious adverse event (SAE) is defined as any AE which:

- results in death,
- is life-threatening, this refers to an event in which the patient was at risk of death at the time of the event; it does not refer to an event that hypothetically might have caused death if more severe,
- requires inpatient hospitalisation or prolongation of existing hospitalisation,
- results in persistent or significant disability or incapacity
- is a congenital anomaly/birth defect,  
or
- is to be deemed serious for any other reason if it is an important medical event when based upon appropriate medical judgment which may jeopardise the patient and may require medical or surgical intervention to prevent one of the other outcomes listed in the above definitions.

Medical and scientific judgement should be exercised in deciding whether other situations should be considered serious reactions, such as important medical events that might not be immediately life threatening or result in death or hospitalisation but might jeopardise the patient or might require intervention to prevent one of the other outcomes listed above.

Examples of such events are intensive treatment in an emergency room or at home for allergic bronchospasm, blood dyscrasias or convulsions that do not result in hospitalisation or development of dependency or abuse. Any suspected transmission via a medicinal product of an infectious agent is also considered a serious adverse reaction.

### AEs considered 'Always Serious'

Cancers of new histology and exacerbations of existing cancer must be reported as a serious event regardless of the duration between discontinuation of the drug and the occurrence of the cancer.

In accordance with the European Medicines Agency initiative on Important Medical Events, Boehringer Ingelheim has set up a list of further AEs, which by their nature, can always be considered to be 'serious' even though they may not have met the criteria of an SAE as given above.

The latest list of 'Always Serious AEs' can be found in the RDC system. A copy of the latest list of 'Always Serious AEs' will be provided upon request. These events should always be reported as SAEs as described above.

### Adverse events of special interest (AESIs)

The term AESI relates to any specific AE that has been identified at the project level as being of particular concern for prospective safety monitoring and safety assessment within this trial, e.g. the potential for AEs based on knowledge from other compounds in the same class. AESI need to be reported to the sponsor's Pharmacovigilance Department within the same timeframe that applies to SAE, please see above.

The following are considered as AESIs in this trial:

- Hepatic injury, as defined by the following alterations of hepatic laboratory parameters:
  - an elevation of AST and/or ALT  $\geq 3$ -fold ULN combined with an elevation of total bilirubin  $\geq 2$ -fold ULN measured in the same blood sample, and/or
  - marked peak aminotransferase (ALT, and/or AST) elevations  $\geq 10$  fold ULN

These lab findings constitute a hepatic injury alert and the patients showing these lab abnormalities need to be followed up according to the 'DILI checklist' provided in the ISF. In case of clinical symptoms of hepatic injury (icterus, unexplained encephalopathy, unexplained coagulopathy, right upper quadrant abdominal pain, etc.) without lab results (ALT, AST, total bilirubin) available, the Investigator should make sure these parameters are analysed, if necessary in an unscheduled blood test. Should the results meet the criteria of hepatic injury alert, the procedures described in the DILI checklist should be followed.

### Intensity of AEs

The intensity of the AE should be judged based on the following:

Mild: Awareness of sign(s) or symptom(s) that is/are easily tolerated

Moderate: Enough discomfort to cause interference with usual activity

Severe: Incapacitating or causing inability to work or to perform usual activities

### Causal relationship of AEs

The definition of an adverse reaction implies at least a reasonable possibility of a causal relationship between a suspected medicinal product and an adverse event. An adverse reaction, in contrast to an adverse event, is characterised by the fact that a causal relationship between a medicinal product and an occurrence is suspected.

Medical judgment should be used to determine the relationship, considering all relevant factors, including pattern of reaction, temporal relationship, de-challenge or re-challenge, confounding factors such as concomitant medication, concomitant diseases and relevant history.

Arguments that may suggest that there is a reasonable possibility of a causal relationship could be:

- The event is consistent with the known pharmacology of the drug
- The event is known to be caused by or attributed to the drug class.
- A plausible time to onset of the event relative to the time of drug exposure.
- Evidence that the event is reproducible when the drug is re-introduced
- No medically sound alternative aetiologies that could explain the event (e.g. pre-existing or concomitant diseases, or co-medications).
- The event is typically drug-related and infrequent in the general population not exposed to drugs (e.g. Stevens-Johnson syndrome).

- An indication of dose-response (i.e. greater effect size if the dose is increased, smaller effect size if dose is diminished).

Arguments that may suggest that there is no reasonable possibility of a causal relationship could be:

- No plausible time to onset of the event relative to the time of drug exposure is evident (e.g. pre-treatment cases, diagnosis of cancer or chronic disease within days / weeks of drug administration; an allergic reaction weeks after discontinuation of the drug concerned)
- Continuation of the event despite the withdrawal of the medication, taking into account the pharmacological properties of the compound (e.g. after 5 half-lives). Of note, this criterion may not be applicable to events whose time course is prolonged despite removing the original trigger.
- Additional arguments amongst those stated before, like alternative explanation (e.g. situations where other drugs or underlying diseases appear to provide a more likely explanation for the observed event than the drug concerned).
- Disappearance of the event even though the study drug treatment continues or remains unchanged.

#### 5.2.2.2 Adverse event collection and reporting

##### AEs collection

Upon enrolment into a trial, the subject's baseline condition is assessed (for instance, by documentation of medical history/concomitant diagnoses), and relevant changes from baseline are noted subsequently.

Subjects will be required to report spontaneously any AEs as well as the time of onset, end, and intensity of these events. In addition, each subject will be regularly assessed by the medical staff throughout the clinical trial and whenever the investigator deems necessary. As a minimum, subjects will be questioned for AEs (and concomitant therapies) at the time points indicated in the [Flow Chart](#). Assessment will be made using non-specific questions such as 'How do you feel?'. Specific questions will be asked wherever necessary in order to more precisely describe an AE.

A careful written record of all AEs shall be kept by the investigator in charge of the trial. Records of AEs shall include data on the time of onset, end time, and intensity of the event as well as any treatment or action required for the event and its outcome.

The following must be collected and documented on the appropriate CRF(s) by the investigator:

[figure not shown]
- From signing the informed consent onwards through the residual effect period (REP), until individual subject's end of trial:
  - All AEs (serious and non-serious) and all AESIs.
  - The only exception to this rule are AEs (serious and non-serious) and AESIs in Phase I trials in healthy volunteers, when subjects discontinue from the trial due to screening failures prior to administration of any trial medication. In

Proprietary confidential information © 2017 Boehringer Ingelheim International GmbH or one or more of its affiliated companies

these cases, the subjects' data must be collected at trial site but will not be entered in the CRF or trial database and will not be reported in the CTR.

- After the individual subject's end of trial:

- The investigator does not need to actively monitor the subject for AEs but should only report relevant SAEs and relevant AESIs of which [REDACTED] may become aware of.

The REP for BI 655130, when measurable drug levels or PD effects are still likely to be present after the last administration, is not known at this early stage of development. Therefore, all AEs reported until the end of trial examination will be considered on treatment; please see [Section 7.3.3](#).

The follow-up period describes the period of time from the last administration of trial medication including the REP until the end of trial examination (last per protocol visit).

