## CLINICAL TRIAL PROTOCOL SYNOPSIS

Name of company: Boehringer Ingelheim		Tabulated Trial Protocol			
Name of finished product: Not applicable					
Name of active ingredient: BI 655130					
Protocol date: 23 Jun 2016	Trial number: 1368.2		Revision date: 02 Aug 2017		
Title of trial: Safety, tolerability, pharmacokinetics and pharmacodynamics of multiple rising intravenous doses of BI 655130 (double-blind, partially randomised within dose groups, placebo-controlled parallel group design) and one single intravenous dose of BI 655130 (single-blind, partially randomised, placebo-controlled) in healthy male subjects					
Principal Investigator: [REDACTED]					
Trial site: [REDACTED]					
Clinical phase: I					
Objectives: To investigate safety, tolerability, pharmacokinetics and pharmacodynamics of single and multiple rising intravenous doses of BI 655130					
Methodology: Multiple rising dose: double-blind, randomised, placebo-controlled within dose groups Single dose: single blind, partially randomised, placebo controlled					
No. of subjects:  total entered: 40 each treatment: 8 per dose group* (6 on active drug and 2 on placebo) * Additional subjects may be entered to allow for testing of intermediate doses on the basis of experience gained during the trial conduct (e.g. preliminary PK data), provided the planned and approved highest dose will not be exceeded. Thus, the actual number of subjects entered may be increased, but will not exceed 48 subjects.					
Diagnosis: Not applicable					
Main criteria for inclusion: Healthy male subjects, age of 18 to 50 years, body mass index (BMI) of 18.5 to 29.9 kg/m 					
Test product: BI 655130 (20 mg/mL) solution for infusion					
dose: Multiple dose: 3 mg/kg, 6 mg/kg, 10 mg/kg and 20 mg/kg body weight Single dose: 20 mg/kg body weight					

Name of company: Boehringer Ingelheim		Tabulated Trial Protocol		
Name of finished product: Not applicable				
Name of active ingredient: BI 655130				
Protocol date: 23 Jun 2016	Trial number: 1368.2		Revision date: 02 Aug 2017	
mode of admin.: Intravenous as 30 min infusion for 3 mg/kg and 6 mg/kg multiple dose Intravenous as 60 min infusion for 10 mg/kg multiple dose and 20 mg/kg single dose Intravenous as 90 min infusion for 20 mg/kg multiple dose				

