## FLOW CHART

Flow Chart (3 mg and 6 mg/kg b.w. dose group, multiple dose)

Visit	Day	Time relative to first drug administration (planned time [h:min])	Approx. time (actual time) [h:min]	Event and comment	$\text{PK}_{\text{plasma}}^4$	$\text{PD}_{\text{blood}}^4$	Plasma ADA 	Safety laboratory/  Urinalysis	Body Temperature	Body Weight	12-lead ECG	ECG monitoring	Vital signs (BP, PR)	Query on adverse events, concomitant therapies 
1	-28 to -3			screening 			X				X		X	
2	-2	-48:00	8:00	ambulatory visit			X 		X					
	-1	-12:00	20:00	admission to trial site			X 							X
1	1	-2:00	6:00		X 	X 	X 	X 	X 		X 		X 	X 
		0:00	8:00	drug administration start of infusion										
		0:15	8:15										X	X
		0:30	8:30	▼ end of infusion 	X	X			X		X 		X	X
		1:00	9:00										X	
		1:30	9:30										X	
		2:00	10:00	light breakfast 					X		X 	▼	X	
		3:00	11:00										X	
		4:00	12:00	Lunch 			X 						X	X 
		6:00	14:00					X		X 			X	
		8:00	16:00	snack (voluntary) 									X	
		10:00	18:00	Dinner 										
		12:00	20:00		X				X		X 		X	X 
		24:00	8:00	Breakfast 	X		X 	X			X 		X	X 
2		28:00	12:00	Lunch 										
		32:00	16:00	snack (voluntary) 				X					X	
		34:00	18:00	Dinner 										X
		48:00	8:00	Breakfast  discharge from trial site (confirmation of fitness  )							X 		X	X
4	72:00	8:00	ambulatory visit				X							X
5	96:00	8:00	ambulatory visit	X										X

Proprietary confidential information © 2017 Boehringer Ingelheim International GmbH or one or more of its affiliated companies

Visit	Day	Event and comment										ECG monitoring	Vital signs (BP, PR)	Query on adverse events, concomitant therapies 
		Time relative to first drug administration (planned time [h:min])	Approx. time (actual time [h:min])	PK plasma 		PD blood 		Plasma ADA 		Laboratory/Urinalysis 		Body Temperature	12-lead ECG	
2	7	156:00	20:00	admission to trial site				X 						X

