## Flow Chart (10 mg/kg b.w. dose group, multiple dose)

Visit	Day	Time relative to first drug administration (planned time [h:min])	Approx. time (actual time) [h:min]	Event and comment		PK plasma 	PD blood 	Plasma ADA 	Safety laboratory/ Urinalysis 	Body Temperature	Body Weight	12-lead ECG	ECG monitoring	Vital signs (BP, PR)	Query on adverse events, concomitant therapies 
1	-28 to -3			screening 				X				X		X	
2	-2	-48:00	8:00	ambulatory visit					X 		X				
	-1	-12:00	20:00	admission to trial site					X 						X
1	1	-2:00	6:00			X 	X 	X 	X 	X 		X 		X 	X 
		0:00	8:00	drug administration start of infusion										▲	
		0:15	8:15											X	X
		0:30	8:30							X				X	X
		1:00	9:00	▼ end of infusion 		X	X			X		X 		X	X
		1:30	9:30											X	
		2:00	10:00	light breakfast 						X		X 	▼	X	
		3:00	11:00											X	
		4:00	12:00	Lunch 				X 						X	X 
		6:00	14:00							X		X 		X	
		8:00	16:00	snack (voluntary) 										X	
		10:00	18:00	Dinner 											
		12:00	20:00			X				X		X 		X	X 
	2	24:00	8:00	Breakfast 		X			X 	X		X 		X	X 
		28:00	12:00	Lunch 											
		32:00	16:00	snack (voluntary) 						X				X	
		34:00	18:00	Dinner 											X
3		48:00	8:00	Breakfast  discharge from trial site (confirmation of fitness  )								X 		X	X
		72:00	8:00	ambulatory visit				X							X
5		96:00	8:00	ambulatory visit		X									X

Proprietary confidential information © 2017 Boehringer Ingelheim International GmbH or one or more of its affiliated companies

Visit	Day	Event and comment		$PK_{plasma}^4$	$PD_{blood}^4$	Plasma ADA 	Laboratory/ Urinalysis 	Body Temperature	12-lead ECG	ECG monitoring	Vital signs (BP, PR)	Query on adverse events, concomitant therapies 
		Time relative to first drug administration (planned time [h:min])	Approx. time (actual time [h:min])									
2	7	156:00	20:00	admission to trial site			$X^{11}$					X
	8	166:00	6:00		$X^2$	$X^2$	$X^2$	$X^{2,10}$	$X^2$	$X^{2,5}$	$X^2$	$X^2$

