## Flow Chart (20 mg/kg b.w. dose group, multiple dose)

Visit	Day	Time relative to first drug administration (planned time [h:min])	Approx. time (actual time) [h:min]	Event and comment		PK plasma 	PD blood 	Plasma ADA 	Safety laboratory/ Urinalysis 	Body Temperature	Body Weight	12-lead ECG	ECG monitoring	Vital signs (BP, PR)	Query on adverse events, concomitant therapies 
1	-28 to -3			screening 				X				X		X	
2	-2	-48:00	8:00	ambulatory visit					X 		X				
	-1	-12:00	20:00	admission to trial site					X 						X
1	1	-2:00	6:00			X 	X 	X 	X 	X 		X 		X 	X 
		0:00	8:00	drug administration start of infusion										▲	
		0:15	8:15											X	X
		0:30	8:30							X				X	X
		1:00	9:00											X	X
		1:30	9:30	end of infusion 	X	X			X		X 			X	X
		2:00	10:00						X		X 	▼	X		
		3:00	11:00	light breakfast 										X	
		4:00	12:00	Lunch 				X 						X	X 
		6:00	14:00						X		X 			X	
		8:00	16:00	snack (voluntary) 										X	
		10:00	18:00	Dinner 											
		12:00	20:00		X				X		X 			X	X 
	2	24:00	8:00	Breakfast 	X			X 	X		X 		X	X 	
		28:00	12:00	Lunch 											
		32:00	16:00	snack (voluntary) 					X					X	
		34:00	18:00	Dinner 											X
3		48:00	8:00	Breakfast  discharge from trial site (confirmation of fitness  )							X 		X	X	
		72:00	8:00	ambulatory visit				X						X	
5		96:00	8:00	ambulatory visit	X									X	

Proprietary confidential information © 2017 Boehringer Ingelheim International GmbH or one or more of its affiliated companies

Visit	Day	Event and comment		$PK_{plasma}^4$	$PD_{blood}^4$	Plasma ADA 	Laboratory/ Urinalysis 	Body Temperature	12-lead ECG	ECG monitoring	Vital signs (BP, PR)	Query on adverse events, concomitant therapies 
		Time relative to first drug administration (planned time [h:min])	Approx. time (actual time [h:min])									
2	7	156:00	20:00	admission to trial site			$X^{11}$					X
	8	166:00	6:00		$X^2$	$X^2$	$X^2$	$X^{2,10}$	$X^2$	$X^{2,5}$	$X^2$	$X^2$

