## Flow Chart (20 mg/kg b.w. dose group, single dose)

dose group, single	Day	Time relative to first drug administration (planned time [h:min])	Approx. time (actual time) [h:min]	Event and comment		PK plasma 	PD blood 	Plasma ADA 	Laboratory/ Urinalysis 	Body Temperature	Body Weight	12-lead ECG	ECG monitoring	Vital signs (BP, PR)	Query on adverse events, concomitant therapies 
1	-28 to -3			screening 				X				X		X	
2	-2	-48:00	8:00	ambulatory visit				X 							
	-1	-12:00	20:00	admission to trial site				X 							X
1	1	-2:00	6:30			X 	X 	X 	X 	X 		X 		X 	X 
		0:00	8:00	drug administration start of infusion										▲	
		0:30	8:30	▼ end of infusion 		X	X			X		X 		X	X 
		1:00	9:00							X		X 		X	X 
		1:30	9:30									X 		X	
		2:00	10:00	light breakfast 		X				X		X 	▼	X	
		2:30	10:30												
		3:00	11:00			X						X 		X	
		4:00	12:00	Lunch 		X			X 			X 		X	X 
		6:00	14:00							X		X 		X	
		8:00	16:00	snack (voluntary) 		X						X 		X	
		10:00	18:00	Dinner 											
		12:00	20:00			X				X		X 		X	X 
	2	24:00	8:00	Breakfast 		X			X 	X		X 		X	X 
		28:00	12:00	Lunch 											
		32:00	16:00	snack (voluntary) 						X		X 		X	
		34:00	18:00	Dinner 											X
3	48:00	8:00	Breakfast  discharge from trial site (confirmation of fitness  )		X							X 		X	X
4	72:00	8:00	ambulatory visit		X			X							X
5	96:00	8:00	ambulatory visit		X										X
8	168:00	8:00	ambulatory visit breakfast (voluntary)		X	X	X	X				X		X	X
15	336:00	8:00	ambulatory visit		X										X
22	504:00	8:00	ambulatory visit breakfast (voluntary)		X	X		X				X		X	X
29	672:00	8:00	ambulatory visit breakfast (voluntary)		X	X	X	X				X		X	X

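### Within the multiple-dose part, early adverse-event queries follow infusion duration (2, 2, 3 and 4 per infusion) while placebo is pooled across all four schedules, so solicited ascertainment of the primary endpoint is not matched

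*Protocol*

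**What the plan says.** The primary endpoint in Protocol 5.2.1 reads: "Primary endpoint to assess safety and tolerability of BI 655130 is the number [N (%)] of subjects with drug-related AEs". Protocol 5.2.2.2 requires subjects to report AEs spontaneously, has medical staff assess them regularly, and adds a floor of solicited questions: "As a minimum, subjects will be questioned for AEs (and concomitant therapies) at the time points indicated in the" Flow Chart. The question itself is open and non-specific. All AEs reported up to the end of trial examination count as on treatment.

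The Synopsis gives the infusion times. For the two lowest doses it reads: "Intravenous as 30 min infusion for 3 mg/kg and 6 mg/kg multiple dose". The other groups run longer: 60 min at 10 mg/kg multiple dose and for the single 20 mg/kg infusion, and 90 min for the 20 mg/kg multiple dose.

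In the AE-query column, the marks after infusion start and before 4:00 are:

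- 3 and 6 mg/kg multiple dose: 0:15, 0:30
- 10 mg/kg multiple dose: 0:15, 0:30, 1:00
- 20 mg/kg multiple dose: 0:15, 0:30, 1:00, 1:30
- 20 mg/kg single dose: 0:30, 1:00

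The next mark is at 4:00 in every chart. The vital-sign column of all three multiple-dose charts is marked at 0:15, 0:30, 1:00, 1:30, 2:00 and 3:00.

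SAP 6.1 analyses all multiple-dose placebo subjects as one group and single-dose placebo subjects separately, and shows the multiple-dose and single-dose results side by side in the safety tables.

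**The concern.** The endpoint is a proportion of subjects, so anything that changes the chance of hearing about an event changes the endpoint. The unequal queries fall in the hours after infusion start, when a plausible time to onset favours calling an event drug-related (Protocol 5.2.2.1). Protocol 3.3.4.1 itself foresees mild, transient infusion reactions such as dizziness, headache and nausea, which are the kind of symptom that may surface only when someone asks. Dose level is known to subjects and investigators (Protocol 3.2 and 4.1.5.1), so assessment along the dose axis is already exposed to observer effects.

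Each placebo subject follows the chart of his own dose group, which would match the questioning within that group. Pooling undoes this: the common placebo column was questioned more often than the 3 and 6 mg/kg groups and less often than the 10 and 20 mg/kg groups. At stake is the descriptive dose pattern in drug-related AEs, which is the main output of the trial.

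**Working it through.** The plan states no figure on this point, so there is nothing to reproduce. The counts come from the Flow Charts.

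**Step 1. Early queries, infusion start to before 4:00.**

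| Group | Infusion (min) | Queries per infusion | Over all infusions |
|---|---|---|---|
| 3 mg/kg multiple | 30 | 2 | 2 × 4 = 8 |
| 6 mg/kg multiple | 30 | 2 | 2 × 4 = 8 |
| 10 mg/kg multiple | 60 | 3 | 3 × 4 = 12 |
| 20 mg/kg multiple | 90 | 4 | 4 × 4 = 16 |
| 20 mg/kg single | 60 | 2 | 2 |

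The four-infusion totals assume that every dosing day repeats the same pattern. Days 1 and 15 are clear in all three multiple-dose charts. The Day 22 rows for 20 mg/kg are incomplete in the text available for review.

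**Step 2. Pooled multiple-dose placebo.** With two placebo subjects per group, the mean is (2 + 2 + 3 + 4)/4 = 2.75 queries per infusion, or 2.75 × 4 = 11 over four infusions.

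**Step 3. Share of all questioning.** After the first dose each infusion has seven further marks (4, 12, 24, 34, 48, 72 and 96 h). Follow-up from Day 29 to Day 176 has ten, since Day 57 carries none. Admission and pre-dose queries before the second, third and fourth infusions add 3 × 2 = 6.

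- 3 and 6 mg/kg: 4 × (2 + 7) + 10 + 6 = 52
- 10 mg/kg: 4 × (3 + 7) + 10 + 6 = 56
- 20 mg/kg: 4 × (4 + 7) + 10 + 6 = 60

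The 20 mg/kg group therefore has 8 more scheduled queries than the 3 mg/kg group, which is 8/52 = 15% more.

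**Step 4. Illustration of scale.** Suppose each relevant query independently elicits an otherwise unreported AE, later judged drug-related, with probability p. Then P(at least one) = 1 − (1 − p)^n. The values of p are assumptions. Two extremes are shown for 3 against 20 mg/kg; differences come from unrounded values.

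| p | All queries equally productive (n = 52 vs 60) | Difference (points) | Only pre-4:00 queries productive (n = 8 vs 16) | Difference (points) |
|---|---|---|---|---|
| 0.0025 | 12.2% vs 13.9% | 1.7 | 2.0% vs 3.9% | 1.9 |
| 0.01 | 40.7% vs 45.3% | 4.6 | 7.7% vs 14.9% | 7.1 |
| 0.02 | 65.0% vs 70.2% | 5.2 | 14.9% vs 27.6% | 12.7 |
| 0.05 | 93.1% vs 95.4% | 2.3 | 33.7% vs 56.0% | 22.3 |

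One subject of six on active drug is 1/6 = 16.7 points. The first extreme stays well below one subject. The second exceeds it only at the largest p shown.

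**The case against.** The strongest reply is that the multiple-dose charts apply one rule: ask at each listed check until the infusion ends. A longer infusion is also a longer period at risk, so some of the extra early capture reflects the regimen. This stands as an account of why the marks differ, and it rules out reading the schedule as tied to dose. It does not remove the mismatch, because infusion duration never falls as dose rises in this part of the trial.

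Second, the queries are a minimum. Subjects must volunteer AEs with onset and end times, AEs are recorded throughout, subjects stay under close surveillance for 48 h, and the open question at 4:00 can still bring out a symptom that has passed. This also stands. It limits any loss to brief symptoms that are neither volunteered nor recalled at 4:00. Unscheduled questioning is not standardised, however, so it cannot be relied on to even out the groups.

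Third, the trial is descriptive, and Protocol 3.2 already admits possible observer bias on dose-dependent effects. That is true and lowers the stakes, but this further difference is avoidable.

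A reader might infer that ascertainment is designed to increase with dose across the trial. The documents do not support that: the 20 mg/kg single-dose group has 2 early queries, as at 3 mg/kg, and fewer than 10 mg/kg multiple dose with the same 60 min infusion. A reader might also compare four queries with two and infer a spurious 20 to 3 mg/kg ratio of 1.5 to 1.8. With an assumed 0.1, 0.2 or 0.3 per query, that compares 34%, 59% or 76% with 19%, 36% or 51%. Those are per-infusion figures for otherwise unreported symptoms. For a symptom recurring at each infusion, the same model over 16 against 8 queries gives ratios of 1.43, 1.17 and 1.06. Neither set is an estimate for the endpoint, and independent chances at successive queries fit a brief symptom poorly.

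**Conclusion.** The point holds within the multiple-dose part. Scheduled early AE queries are 2, 2, 3 and 4 per infusion (8, 8, 12 and 16 over four, if all dosing days follow the pattern), and pooled placebo averages 2.75. Solicited ascertainment is therefore unequal between dose groups and between each dose group and its comparator. It can cause a modest solicitation bias in the primary endpoint for brief, unvolunteered infusion-day symptoms, in the direction of more events at 10 and 20 mg/kg than at 3 and 6 mg/kg.

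The size cannot be derived from the documents. The illustrative differences above rest on assumed elicitation probabilities, independence between queries, and a choice of which queries matter. The single-dose group is compared with its own placebo on the same chart, so that comparison is matched; only its side-by-side display with the multiple-dose groups needs the caution.

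**What to change.** In every multiple-dose Flow Chart, mark the same AE query at 0:15, 0:30, 1:00, 1:30, 2:00 and 3:00 after infusion start on Days 1, 8, 15 and 22, attached to the vital-sign checks already scheduled then. This makes six early queries in each group, so the addition per dosing day is 6 − 2 = 4 at 3 and 6 mg/kg, 6 − 3 = 3 at 10 mg/kg and 6 − 4 = 2 at 20 mg/kg. The cost is Flow Chart marks, CRF lines and those few questions. No visit, staff or sample is added.

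For groups already dosed, state the schedule difference in the clinical trial report beside the primary table. Add to SAP 7.8.1 a separate tabulation of drug-related AEs with recorded onset within 4 h of infusion start. Use onset time for this: Protocol 5.2.2.2 requires it to be recorded but does not list how an event was elicited, so a split by solicited against volunteered may not be possible. The tabulation shows how much of any dose pattern comes from the affected window. It cannot recover events that were never reported.
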